### Clinical Investigational Plan

#### 1.0 SYNOPSIS

Title:	Burst Optimized Stimulation Study
Acronym:	BOSS
Purpose:	This purpose of this study is to evaluate the therapeutic efficacy of energy efficient burst microdosing stimulation paradigms in patients with chronic pain.
Primary Objectives:	To compare differences in therapeutic efficacy between conventional burst stimulation parameters (Burst train consisting of 5 pulses, Intraburst frequency: 500 Hz, Burst Rate: 40 Hz, Pulse width: 1000 μs) and energy efficient burst microdosing stimulation paradigms listed below: 
 
• Standard burst stimulation parameters with 5 seconds of STIM ON, followed by 5 seconds of STIM OFF
 
• Standard burst stimulation parameters with 5 seconds of STIM ON, followed by 10 seconds of STIM OFF
 

Secondary Objectives:	To compare differences in: 
 
• Quality of life
 
• Subject satisfaction
 
• Patient preference
 
• Incidence of adverse events
 
 
between standard burst stimulation and the two different burst microdosing paradigms.

Primary Endpoints:	
 
• Change in Visual Analog Scale (VAS) between baseline and follow up visits
 

Secondary Endpoints	Difference in 
 
• Quality of life (EQ-5D)
 
• Subject satisfaction
 
• Incidence rate of adverse events
 
 
between standard burst stimulation and the two different burst microdosing paradigms

## Clinical Investigational Plan

### Design:

This is a prospective, multicenter, randomized, double-blinded crossover study designed to compare conventional burst stimulation parameters to two different burst microdosing paradigms.

Subjects previously implanted with any market released St. Jude Medical (SJM) spinal cord stimulator for control of chronic intractable pain associated with a diagnosis of failed back surgery syndrome or neuropathic back and/or leg pain and currently using only burst stimulation parameters for at least 3 months will be considered for inclusion in this study.

After signing the informed consent, subjects will be screened. Subjects will be randomized 1:1:1 to one of the three treatment sequences:

#### *Group 1:*

- Standard burst
- 5 seconds STIM ON, 5 seconds STIM OFF, standard burst parameters
- 5 seconds STIM ON, 10 seconds stim OFF, standard burst parameters

#### *Group 2:*

- 5 seconds STIM ON, 5 seconds STIM OFF, standard burst parameters
- 5 seconds STIM ON, 10 seconds stim OFF, standard burst parameters
- Standard burst

#### *Group 3:*

- 5 seconds STIM ON, 10 seconds stim OFF, standard burst parameters
- Standard burst
- 5 seconds STIM ON, 5 seconds STIM OFF, standard burst parameters

Subjects will be programmed accordingly and will receive a one-week pain diary to evaluate the pain level during the first stimulation paradigm.

After two weeks the subjects will return for the first follow up visit and complete questionnaires and assessments to evaluate pain, quality of life and satisfaction for the first stimulation paradigm. Subsequently subjects will be programmed with the second paradigm according to group assignment and will receive a one-week pain diary.

After two weeks, subjects will return for the second follow up visit and complete questionnaires and assessments to evaluate the therapeutic efficacy of the second stimulation paradigm. Subjects will then be programmed with the third stimulation paradigm according to group assignment and receive a one-week pain diary.

### Clinical Investigational Plan

	
After two weeks, subjects will return for the third follow up visit and complete questionnaires and assessments to evaluate the therapeutic efficacy of the third stimulation paradigm. Subjects will express their preference between the three burst stimulation paradigms, their IPGs will be programmed accordingly and they will exit the study.
 
Primary and secondary assessments will be compared between baseline and the two follow up visits.
 
The total duration of the study is expected to be 6 months.
 
The study will be conducted in a maximum of 4 centers in Europe

Devices used:	
Any commercially available SJM neurostimulation system:
 
 
• Implantable Pulse Generator (IPG)
 
• IPG Charger (in case of a rechargeable IPG)
 
• Clinician Programmer
 

Study Population	
The study population will consist of patients with chronic pain for failed back surgery syndrome or neuropathic back and/or leg pain with an implanted commercially available SJM spinal cord stimulation device and have been using conventional burst stimulation parameters for the past three months (Burst train consisting of 5 pulses, Intraburst frequency: 500 Hz, Burst rate: 40 Hz, Pulse width: 1000 μs). Up to 40 subjects will be enrolled in this study in up to 4 centers. Of these, it is expected that 30 subjects will be successfully screened and complete the study.
 
Patients will be considered for enrollment by the Principal Investigator as a candidate for the study at the study site if they meet the inclusion/exclusion criteria requirements, and agree to participate in the study.

Inclusion/Exclusion Criteria	
Inclusion Criteria
 
 
• Subject has been implanted with a commercially available SJM spinal cord stimulator for controlling chronic intractable pain associated with back and/or leg pain;
 
• Subject has been exclusively using burst stimulation for at least three months;
 
• Subject is 18 years of age or older;
 
• Subject’s pain-related medication regimen was stable in the 4 weeks prior to the screening evaluation;
 
• Subject agrees not to add or increase pain-related medication from enrollment through the study duration;
 
• Subject is willing to cooperate with the study requirements including compliance with the regimen and completion of all office visits;
 

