**Clinical Investigational Plan**

[figure not shown]
	
Exclusion Criteria
 
 
• Subject is currently participating in a clinical investigation study that includes an active treatment arm;
 
• Subject is currently receiving, applying or considering seeking workers compensation, or is involved in disability litigation;
 
• Subject has a non SJM neuromodulation device
 

Data Collection	
Subsequent to receiving the informed consent, subjects will be screened for inclusion/exclusion criteria. Eligible subjects will be randomized 1:1:1 to one of the treatment groups and be programmed accordingly. Subjects will be provided with a one-week diary to assess the pain relief provided by the first stimulation paradigm.
 
During the first follow up visit, the subjects will evaluate the pain level experienced during standard burst stimulation using the Visual Analog Scale (VAS), the European Quality of Life-5 Dimension (EQ-5D) questionnaire and the subject satisfaction questionnaire. Subjects will be programmed to the second stimulation paradigm and will be provided with a one-week pain diary.
 
During the second follow up visit, subjects will evaluate the efficacy of the second stimulation paradigm using the same assessments used in the first follow up visit. Subjects be programmed with the third stimulation paradigm and will be provided with a one-week pain diary.
 
During the third follow up visit, subjects will evaluate the efficacy of the last stimulation paradigm using the same assessments used in previous follow up visits. Additionally, subjects will be asked to express their preference between the three stimulation paradigms.
 
Occurrence of adverse events will be recorded through the study duration.

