## Clinical Investigational Plan

### 6.2 PROCEDURES

The clinical study will be conducted in accordance with the CIP. All parties participating in the conduct of the clinical study will be qualified by education, training, or experience to perform their tasks and this training will be documented appropriately.

The clinical study will not commence until St. Jude Medical receives written approval from the EC and relevant regulatory authorities and all required documents have been collected from the site(s).

Table 1: List of all study specific activities/procedures

Study Activity	Visit	Screening	Follow up visit 1	Follow up visit 2	Follow up visit 3
Informed Consent		X			
Inclusion/Exclusion Criteria Screening		X			
Randomization		X			
Sequester patient programmer		X			
Return patient programmer					X
Provide pain diary		X	X	X	
Collect pain diary			X	X	X
VAS assessment			X	X	X
EQ-5D questionnaire			X	X	X
Subject satisfaction questionnaire			X	X	X
Collect programming parameter printouts			X	X	X
Stimulation reprogramming		X	X	X	
Document patient preference					X
Program preferred stimulation paradigm					X

Table 2: Visits Timeline

Visit	Screening	Follow up visit 1	Follow up visit 2	Follow up visit 3
Timing	At enrollment	14±5 days after screening visit	14±5 days after follow up visit 1	14±5 days after follow up visit 2

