## Clinical Investigational Plan

### 6.4 FOLLOW UP VISIT 1

During the baseline visit, the investigator will collect the pain diary provided at the screening visit and record the current stimulation parameters in the parameters form. The subject will rate the pain during the first stimulation paradigm using the VAS, the EQ-5D and the satisfaction questionnaires administered by a clinician blinded to the stimulation paradigm. Subject’s stimulators will be programmed with the second stimulation paradigm according to the group assignment. Stimulation intensity will gradually be increased until the subject perceives the stimulation to find the Threshold for Perception (TP), and then the intensity will subsequently be reduced to the sub-perception level providing optimal pain relief. Subjects will be provided with a new pain diary for the assessment of the new stimulation paradigm. One week after this visit, the subject will be contacted to schedule the second follow up visit and instructed to start recording pain levels on the pain diary

The following activities and assessments will be performed during the first follow up visit.

Timing of visit	Activities at visit	Case Report Form
Follow up 1	
 
Collect pain diary
 
Programming parameters printout
 
Subject fills out pain assessment and quality of life questionnaires
 
Provide pain diary
 
Program IPG with second stimulation paradigm according to group assignment
 
	
 
VAS Form
 
EQ-5D Form
 
User Satisfaction Form
 
Parameters Form
 

### 6.5 FOLLOW UP VISIT 2

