### 12.0 STATISTICAL CONSIDERATIONS

#### 12.1 STATISTICAL DESIGN, HYPOTHESES, METHOD AND ANALYTICAL PROCEDURES

During baseline visit subjects will be randomized 1:1:1 to one of the three treatment sequences. An envelope-based system will be used for identifying which group the subject has been assigned. St. Jude Medical will provide sealed envelopes containing the site number and subject ID/sequence number. Inside the envelope, the randomization assignment will be identified along with the site number and subject ID/sequence number.

During reprogramming the subjects will not be made aware of what paradigm is currently being programmed. Pain questionnaires (VAS, EQ-5D, satisfaction and stimulation preference) will be administered by a clinician blinded to the currently programmed stimulation paradigm.

Scores from the subject's questionnaires as well as subject satisfaction will be compared between follow up visits using a repeated measure ANOVA under the hypothesis of equivalence between standard and burst microdosing stimulation paradigms.

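### The synopsis comparison rule names baseline plus two follow-up visits in a three-visit crossover, and under neither meaning of baseline in the plan does it compare standard burst with both microdosing paradigms as the objective needs

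*Combined protocol and SAP*

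**What the plan says.** The Design part of the synopsis states the rule: "Primary and secondary assessments will be compared between baseline and the two follow up visits". Shortly before it, the same text describes a third scored visit: "After two weeks, subjects will return for the third follow up visit and complete questionnaires and assessments". The Data Collection part agrees: "During the third follow up visit, subjects will evaluate the efficacy of the last stimulation paradigm". Table 2 in section 6.2 schedules that visit "14±5 days after follow up visit 2", and the row "VAS assessment" in Table 1 is marked three times.

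Baseline has two meanings:

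- Section 6.4, headed as follow-up visit 1: "During the baseline visit, the investigator will collect the pain diary provided at the screening visit".
- Section 12.1: "During baseline visit subjects will be randomized 1:1:1 to one of the three treatment sequences". Table 1 places randomisation at screening. The activity and form list for screening in section 6.3 contains no VAS or EQ-5D.

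The primary endpoint (synopsis and section 4.4.1) is a change in VAS from baseline to follow-up, with no count of visits. Section 12.1 says that questionnaire and satisfaction scores "will be compared between follow up visits using a repeated measure ANOVA", under a hypothesis of equivalence between standard and microdosing stimulation. It sets no limit of two visits and names no period term. Appendix B shows a first release, so all of this is current text.

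**The concern.** Each follow-up visit scores a different paradigm, and the order depends on the sequence. A rule that refers to baseline and two visits therefore has to say which visits are meant and what the reference is. The plan does not settle either.

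The primary objective is standard burst against each of two microdosing paradigms. An analyst who followed the synopsis could leave out a third of the scores, or could measure change from a visit at which two of the three groups were not on standard burst. Section 12.2 says that the study is meant to yield early estimates of effect size, so both the precision and the meaning of those estimates matter.

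**Working it through.** **Inputs.** The sequences are in the synopsis and section 4.2. Section 12.2 expects 30 completers. I assume 10 per sequence, from the 1:1:1 allocation. The plan gives no SD, margin, effect size or power, so there is no figure to reproduce; results are in units of the within-subject variance σ². The model is additive in subject, period and paradigm, without carryover. Write S for standard burst, M1 for 5 s on / 5 s off, and M2 for 5 s on / 10 s off.

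| | Visit 1 | Visit 2 | Visit 3 |
|---|---|---|---|
| Group 1 | S | M1 | M2 |
| Group 2 | M1 | M2 | S |
| Group 3 | M2 | S | M1 |

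**1. All three visits used.** There are 30 × 3 = 90 scores, and every pair of paradigms is observed in all 30 subjects. Each paradigm occurs equally often at each visit, so the contrast variance is 2σ²/30 = 0.067σ².

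**2. Baseline is screening, and two of the three visits are compared.** 30 × 2 = 60 scores are used and 30 are not. If visit 3 is the one omitted, Group 1 loses M2, Group 2 loses S and Group 3 loses M1. Each paradigm is then seen in 20 of 30 subjects. Each pair is seen together in only one group, so in 10 of 30 subjects and always in the same order.

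Let δ be the period 1 minus period 2 effect. The group mean differences (visit 1 minus visit 2) estimate:

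- D1 = S − M1 + δ
- D2 = M1 − M2 + δ
- D3 = M2 − S + δ

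Each has variance 2σ²/10 = 0.2σ². The paradigm terms sum to zero, so (D1 + D2 + D3)/3 estimates δ. The period-adjusted estimate of S − M1 is

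D1 − (D1 + D2 + D3)/3 = (2/3)D1 − (1/3)D2 − (1/3)D3,

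with variance 0.2σ² × (4/9 + 1/9 + 1/9) = 0.133σ².

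The variance ratio is 0.133/0.067 = 2, and the standard error ratio is √2 = 1.41. Since 2/15 = 0.133, the precision equals that of 15 subjects in the full design. A least-squares fit gave 0.133 for each of the three possible choices of two visits, and for both microdosing contrasts. A simple paired difference in the 10 subjects (D1 alone) would also carry δ.

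On this meaning, the baseline side of the comparison has no scheduled VAS or EQ-5D score.

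**3. Baseline is follow-up visit 1.** Baseline plus visits 2 and 3 covers all 90 scores. The paradigm content of the changes is:

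| | Visit 2 − visit 1 | Visit 3 − visit 1 |
|---|---|---|
| Group 1 | M1 − S | M2 − S |
| Group 2 | M2 − M1 | S − M1 |
| Group 3 | S − M2 | M1 − M2 |

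Only Group 1 has standard burst as the reference. Each column sums to zero, so with equal groups the pooled change from visit 1 contains the period difference and no paradigm effect.

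**4. Section 12.1 taken literally.** With equal groups, every visit mean is (S + M1 + M2)/3 plus its period effect. If visit is the ANOVA factor, the comparison is between periods and not between paradigms.

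**The case against.** The strongest case is that this is one loose synopsis sentence. Section 12.1 is the statistical section and has no two-visit limit; nor does the primary endpoint in the synopsis or in section 4.4.1. The objectives require both microdosing paradigms to be compared with standard burst, and the hypothesis in section 12.1 is about paradigms, so the intention is clear. Section 6.4 calls follow-up visit 1 baseline, and on that usage nothing is dropped. It is also the only one of the two meanings with a scheduled VAS score. The wording may be left from a fixed-order plan: the synopsis Data Collection text describes the first follow-up as standard burst, and section 6.5 describes the second as the first microdosing paradigm, both true only for Group 1. That origin is an inference.

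Much of this stands. A reader might infer that the plan discards one paradigm in every subject whichever two visits are meant, and so runs with a 41% larger standard error. The documents do not support that: it holds only if baseline is screening and the synopsis sentence governs, and no section says which visit would be omitted. Nor is a power target missed, because section 12.2 sets none.

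The objection does not rescue the rule. Taking visit 1 as baseline avoids the loss only by using a reference that differs between groups. Section 12.1 avoids the two-visit limit but names visits, not paradigms, as what is compared.

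**Conclusion.** The point holds as an inconsistency that should be corrected. The synopsis rule does not fit a three-visit crossover, and neither meaning of baseline makes it answer the primary objective. On the screening meaning, 30 of 90 scores go unused and the contrast variance doubles from 0.067σ² to 0.133σ². This is a conditional cost, resting on 10 completers per sequence and the additive model above. On the visit 1 meaning the loss is zero, but the reference is S, M1 or M2 according to group. Section 12.1 leaves the matter open, because visits in these rotating sequences are periods.

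**What to change.** - **Synopsis and section 12.1:** state that all primary and secondary scores from follow-up visits 1, 2 and 3 are analysed by assigned paradigm, each microdosing paradigm against standard burst, in a model with subject, period and paradigm terms.
- **Baseline wording:** reconcile the primary endpoint (synopsis and section 4.4.1), section 6.4 and section 12.1 with that statement, so that baseline has one meaning or is not used in the comparison. The paradigm contrast does not need it: for a common pre-treatment score b, (M1 − b) − (S − b) = M1 − S.

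The cost is wording changes in these places and a small change to the analysis model. No visit, subject or assessment is added.

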**Clinical Investigational Plan**

[figure not shown]
	
Exclusion Criteria
 
 
• Subject is currently participating in a clinical investigation study that includes an active treatment arm;
 
• Subject is currently receiving, applying or considering seeking workers compensation, or is involved in disability litigation;
 
• Subject has a non SJM neuromodulation device
 

Data Collection	
Subsequent to receiving the informed consent, subjects will be screened for inclusion/exclusion criteria. Eligible subjects will be randomized 1:1:1 to one of the treatment groups and be programmed accordingly. Subjects will be provided with a one-week diary to assess the pain relief provided by the first stimulation paradigm.
 
During the first follow up visit, the subjects will evaluate the pain level experienced during standard burst stimulation using the Visual Analog Scale (VAS), the European Quality of Life-5 Dimension (EQ-5D) questionnaire and the subject satisfaction questionnaire. Subjects will be programmed to the second stimulation paradigm and will be provided with a one-week pain diary.
 
During the second follow up visit, subjects will evaluate the efficacy of the second stimulation paradigm using the same assessments used in the first follow up visit. Subjects be programmed with the third stimulation paradigm and will be provided with a one-week pain diary.
 
During the third follow up visit, subjects will evaluate the efficacy of the last stimulation paradigm using the same assessments used in previous follow up visits. Additionally, subjects will be asked to express their preference between the three stimulation paradigms.
 
Occurrence of adverse events will be recorded through the study duration.

## Clinical Investigational Plan

### 2.0 BACKGROUND AND JUSTIFICATION FOR CLINICAL STUDY

Spinal cord stimulation (SCS) is increasingly being used as an alternative for the treatment of chronic, intractable pain. In a systematic meta-analysis of the literature, Taylor et al. (2006) reported that SCS reduces pain, improves quality of life, reduces analgesic use, allows some patients to return to work and may also result in significant cost savings over time, while having minimally significant adverse events in patients with neuropathic back and/or leg pain.

Patients receiving conventional tonic SCS (electrical pulses delivered in the 40-60Hz stimulation frequency range) experience paresthesia or a tingling sensation. Burst SCS is a newer paradigm that is currently approved for use in the European Union and Australia to treat chronic pain conditions. Burst stimulation eliminates or greatly reduces the incidence of paresthesia (Courtney *et al.* 2014), and it entails delivering groups of pulses called burst trains (A) repeated at a burst rate (B); within each burst train, several pulses are issued at an intra-burst rate (C) (See Figure 1). Individual pulses are characterized by a pulse amplitude (D) and pulse width.

**Figure 1: Burst Pattern**

While the efficacy of standard burst stimulation parameters is known (Courtney et al. 2014, DeRidder et al., 2010, 2013), its comparison to more energy efficient settings is unknown.

Burst microdosing consists of delivery of intermittent doses of burst stimulation. Although there is no published information on the therapeutic efficacy of burst microdosing, anecdotal observations lead us to hypothesize its use could result in a similar clinical outcome compared to standard burst stimulation.

Use of these new energy efficient stimulation parameters has the potential to prolong the battery life of a non-rechargeable, primary cell Implantable Pulse Generator (IPG) by approximately

## Clinical Investigational Plan

100% or more. It also has the potential to improve patient convenience by decreasing the frequency with which the patient has to recharge a non-primary cell IPG.

In this study, we aim to compare the therapeutic efficacy of standard burst stimulation parameters (Burst train consisting of 5 pulses, Intraburst frequency = 500 Hz, Burst Rate = 40 Hz, Pulse width = 1000  $\mu$ s) to the following energy efficient burst microdosing stimulation parameters:

- Standard burst stimulation parameters with 5 seconds of STIM ON, followed by 5 seconds of STIM OFF
- Standard burst stimulation parameters with 5 seconds of STIM ON, followed by 10 seconds of STIM OFF

